### 6.1.3. Health Assessment Questionnaire Disability Index (HAQ-DI)

The HAQ-DI score is defined as the average of the scores of eight functional categories (dressing and grooming, arising, eating, walking, hygiene, reach, grip, and other activities), administered by the patient. Responses in each functional category are collected as: without any difficulty; with some difficulty; with much difficulty; unable to do a task in that area and with or without aids or devices. The HAQ-DI score ranges from 0 (no disability) to 3 (completely disabled), when 6 or more categories are non-missing. Detailed algorithm for calculating HAQ-DI score is described in [Appendix 2](#).

HAQ-DI also includes a separate pain assessment and subject will be requested to mark the severity of the pain in the past week on a 0-100 VAS, with 0 indicating “no pain” and 100 indicating “severe pain”.

## 6.2. Primary Efficacy Endpoint

The primary efficacy endpoint is the proportion of subjects who achieve ACR20 response at Week 24.

### 6.2.1. Definition of the Primary Efficacy Endpoint

A subject achieves ACR20 response when this subject has

- $\geq 20\%$  improvement from baseline in TJC68, AND
- $\geq 20\%$  improvement from baseline in SJC66, AND
- $\geq 20\%$  improvement from baseline in at least 3 of the following 5 items:
  - a) PGA
  - b) SGA
  - c) Subject's pain assessment
  - d) HAQ-DI score
  - e) hsCRP

Percent improvement from baseline at a postbaseline visit is calculated as follows for all 7 components mentioned above:

$$\% \text{ improvement} = \frac{\text{baseline value} - \text{postbaseline value}}{\text{baseline value}} \times 100$$

If the baseline value is 0, then the percent improvement from baseline is set to missing.

In the case that some ACR20 components are missing other than TJC68 or SJC66, the ACR20 assessment will be based on the non-missing components. If non-missing components are not sufficient to determine ACR20 response, then the ACR20 response will be considered as missing.

### 6.2.2. Statistical Hypothesis for the Primary Efficacy Endpoint

In the primary analysis, the ACR20 response rate at Week 24 in the filgotinib 200 mg in combination with MTX group will be compared to MTX alone group for a superiority test at the 2-sided 0.05-level. If we denote the ACR20 response rate at Week 24 in the filgotinib 200 mg in combination with MTX group and MTX alone group as  $P_1$  and  $P_2$ , respectively, the null and alternative hypotheses for the superiority test on the primary efficacy endpoint are as follows:

$$H_0: P_1 = P_2;$$

vs

$$H_1: P_1 \neq P_2.$$

### **6.2.3. Primary Analysis of the Primary Efficacy Endpoint**

To test for superiority of filgotinib 200 mg in combination with MTX group versus MTX alone group in proportion of subjects who achieve ACR20 at Week 24, a logistic regression analysis with treatment groups and stratification factors in the model will be used. Subjects who do not have sufficient measurements to establish efficacy at Week 24 will be considered as failures (ie, NRI). The p-value from the logistic regression model for testing the superiority of filgotinib 200 mg in combination with MTX as compared to MTX alone will be provided. The 2-sided 95% confidence interval (CI) of the ACR20 response rate at Week 24 based on normal approximation for each treatment group will be provided for each treatment group. In addition, non-stratified ACR20 response rate difference between treatment groups with its 95% CI based on the normal approximation will be provided.

The comparisons of other filgotinib dose groups versus MTX alone group in proportion of subjects achieving ACR20 at Week 24 will also be conducted with the similar logistic regression model with NRI.

The number and percentage of ACR20 nonresponders observed and nonresponders due to missing at Week 24 will be summarized respectively by treatment groups.

For subjects with observed ACR20 outcomes (ie, responders and observed nonresponders) at Week 24, actual values and change from Baseline at Week 24 in individual components, including TJC68, SJC66, SGA, PGA, Subject's Pain Assessment, and hsCRP, will be summarized by using descriptive statistics (sample size, mean, SD, median, Q1, Q3, minimum, and maximum) by treatment groups.

The proportions of subjects achieving ACR20 (using NRI) will be plotted over time by treatment.

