## 1.2. Study Design

[figure not shown]
This is a randomized, double-blind, placebo- and active-controlled, add-on, Phase 3 study in adult male and female subjects with moderately to severely active RA who have limited or no prior exposure to MTX therapy. The study is designed to evaluate the efficacy, safety and tolerability of filgotinib as well as its effect on patient-reported outcomes, including work productivity, fatigue, and quality of life. In addition, PK will be assessed.

Approximately 1200 subjects will be randomized in a 2:1:1:2 ratio to filgotinib 200 mg plus MTX, filgotinib 100 mg plus MTX, filgotinib 200 mg alone, or MTX alone, for up to 52 weeks:

- Filgotinib 200 mg + MTX group: filgotinib (200 mg once daily [q.d.]) + PTM filgotinib 100 mg (PTM q.d.) + MTX (once weekly up to 20 mg) (N=400)
- Filgotinib 100 mg + MTX group: filgotinib (100 mg q.d.) + PTM filgotinib 200 mg (PTM q.d.) + MTX (once weekly up to 20 mg) (N=200)
- Filgotinib 200 mg monotherapy group: filgotinib (200 mg q.d.) + PTM filgotinib 100 mg (PTM q.d.) + PTM MTX (PTM once weekly) (N=200)
- MTX monotherapy group: PTM filgotinib 100 mg (PTM q.d.) and PTM filgotinib 200 mg (PTM q.d.) + MTX (once weekly up to 20 mg) (N=400)

Randomization will be stratified by geographic region and presence of rheumatoid factor (RF) or anti-cyclic citrullinated peptide antibody (anti-CCP Ab) at screening.

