## 6.3.2. Analysis Methods for Key Secondary Efficacy Endpoints

Hypothesis testing on the key secondary efficacy endpoints will commence after the testing on the primary efficacy endpoint reaches statistical significance, and will be performed according to the hierarchical testing principle at the 2-sided 0.05 level as described in Section 3.5. If a null hypothesis is not rejected, formal sequential testing will be stopped and only nominal significance will be reported for the remaining hypotheses.

For proportion of subjects who achieve  $\text{DAS28(CRP)} < 2.6$  at Week 24, the similar logistic regression analysis with the same model specification as the primary endpoint analysis described in Section 6.2.3 will be adopted for the comparisons between treatment groups. The NRI method will be used to impute missing values. Comparisons will be made between each filgotinib dose group and the MTX alone group. The p-value from the logistic regression model will be reported for statistical inference. The 2-sided 95% CI of the response rate of  $\text{DAS28(CRP)} < 2.6$  at Week 24 based on normal approximation will be provided for each treatment group. In addition, non-stratified response rate difference between treatment groups with its 95% CI based on the normal approximation will be provided.

The change from Baseline in HAQ-DI at Week 24 will be analyzed using the mixed-effects model for repeated measures (MMRM) that include all available data at postbaseline visits. Subjects that have a baseline value and at least one postbaseline value are included in the analysis. The MMRM model will be used to evaluate treatment effect on change score from Baseline, with baseline value, stratification factors, treatment, visit, and treatment by visit interaction included as fixed effects and subject being the random effect. An unstructured variance-covariance matrix will be used. The Kenward-Roger method will be used to estimate the degrees of freedom. Missing change scores due to missing study visits or early withdrawal will not be otherwise imputed using the MMRM approach. The least squares (LS) means along

with the two-sided 95% CIs and the p-value for the difference in mean change from Baseline in HAQ-DI at Week 24 between each filgotinib dose group and MTX alone group from MMRM will be provided.

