## 6.5. Changes From Protocol-Specified Efficacy Analyses

The following changes were made from the protocol-specified efficacy analyses:

- It has been observed from the blinded data that the enrollment rate is low in some combinations of stratification factors, which will result in a small cell counts for the Cochran- Mantel-Haenszel test adjusted for the stratification factors. The logistic regression analysis with treatment and stratification factors in the model will be used instead to analyze binary endpoints.
- The following two endpoints have been updated as key secondary efficacy endpoints in Section 6.3 and included in the hierarchy testing in Section 3.5, in order to support inclusion in the label.
  - Change from Baseline in SF-36 PCS at Week 24
  - Change from Baseline in FACIT-Fatigue at Week 24
- Given the importance of determining the lowest effective dose for filgotinib in RA, the hierarchical ordering has been updated in Section 3.5 to test filgotinib 100 mg in combination with MTX immediately after each test for filgotinib 200 mg in combination with MTX (including the primary endpoint and each of the key secondary endpoints). In addition, the testing for ACR20, HAQ-DI, and mTSS is moved up earlier in the list to accommodate the changes aforementioned as well as because of the importance of these endpoints in determining drug efficacy in RA. These changes together caused a relative move down for testing of DAS28(CRP)  $<$  2.6.

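### For ACR20 and DAS28(CRP) < 2.6 the test is adjusted for the randomisation strata but the only interval for the treatment difference is not: a valid, at most mildly conservative interval that is free to improve

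*SAP*

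**What the plan says.** Randomisation is stratified by geographic region (five groups, A to E) and by presence of RF or anti-CCP antibody, so there are up to 10 cells (SAP 1.2 and 3.3). SAP 3.3 says that these factors will enter the efficacy models as covariates.

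For the primary endpoint, SAP 6.2.3 states that "a logistic regression analysis with treatment groups and stratification factors in the model will be used", and the superiority p-value comes from that model. As an addition it plans that "non-stratified ACR20 response rate difference between treatment groups with its 95% CI based on the normal approximation will be provided". For DAS28(CRP) < 2.6, SAP 6.3.2 says "The p-value from the logistic regression model will be reported for statistical inference", and again that "non-stratified response rate difference between treatment groups with its 95% CI based on the normal approximation will be provided". For neither endpoint does the SAP plan an adjusted odds ratio with its interval, or a stratum-adjusted or standardised risk difference.

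The continuous key secondary endpoints (HAQ-DI, mTSS, SF-36 PCS, FACIT-Fatigue) are treated differently. Estimate, 95% CI and p-value all come from one stratum-adjusted MMRM (SAP 6.3.2).

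SAP 6.5 explains why logistic regression replaced the Cochran-Mantel-Haenszel test: blinded data showed that "the enrollment rate is low in some combinations of stratification factors". It gives no reason for leaving the interval unstratified.

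**The concern.** The test and the effect estimate for the same comparison come from two different analyses. Stratified randomisation balances the strata across arms. If the strata predict response, the crude variance p(1-p)/n still counts the between-stratum variation that the design has removed from the comparison, so the crude interval is wider than the design requires. A success on the adjusted test could then stand beside an interval that includes zero.

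SAP 6.2.2 states the hypothesis on response rates, so the risk difference is the natural effect measure. The pattern affects six tests in the SAP 3.5 sequence, counting the primary: two binary endpoints by three filgotinib groups. Four of the six use a 200-subject arm.

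**Working it through.** **Inputs from the documents.** ACR20 planning rates 62% (MTX) and 78% (each filgotinib group); 400 subjects for filgotinib 200 mg + MTX and for MTX, 200 for each of the other two groups; two-sided 0.05 (SAP 1.3, 6.2.2). **Not in the documents, so assumed:** stratum sizes, stratum response rates, and the DAS28(CRP) < 2.6 rates.

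**The plan's own figure.** Power = Φ[(0.16 - 1.96 × SE0)/SE1], where SE0 is the pooled standard error under the null and SE1 the unpooled one.
- 400 vs 400: SE0 = √(2 × 0.70 × 0.30/400) = 0.0324 and SE1 = √[(0.1716 + 0.2356)/400] = 0.0319, so power is 99.9%.
- 200 vs 400: SE0 = 0.0406 and SE1 = 0.0380, so power is 98.3%.

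Both agree with the SAP's statement of over 90%.

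**Width.** Let s be the SD of response rates between strata, the same in both arms, with strata balanced across arms.
- Crude variance = p1(1-p1)/n1 + p0(1-p0)/n0.
- Stratified variance = [p1(1-p1) - s²]/n1 + [p0(1-p0) - s²]/n0.
- Half-width = 1.96 × √variance.

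For 78% vs 62%, the crude half-width is 1.96 × √(0.4072/400) = 6.25 points at 400 vs 400, and 1.96 × √(0.1716/200 + 0.2356/400) = 7.46 points at 200 vs 400. At s = 15 points the 400 vs 400 figure becomes 1.96 × √[(0.4072 - 0.045)/400] = 5.90.

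| Assumed s (points) | Stratified half-width, 400 vs 400 | Crude wider by | Stratified half-width, 200 vs 400 | Crude wider by |
|---|---|---|---|---|
| 0 | 6.25 | 0% | 7.46 | 0% |
| 3 | 6.24 | 0.2% | 7.44 | 0.2% |
| 5 | 6.22 | 0.6% | 7.41 | 0.7% |
| 10 | 6.10 | 2.6% | 7.26 | 2.7% |
| 15 | 5.90 | 6.0% | 7.01 | 6.4% |

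With r the width ratio, coverage of the crude interval is 2Φ(1.96 r) - 1. At 400 vs 400 this is 95.6% for s = 10 and 96.2% for s = 15.

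For DAS28(CRP) < 2.6 with assumed rates of 45% vs 30% and 400 per arm, the crude half-width is 1.96 × √(0.4575/400) = 6.63 points. At s = 15 the stratified one is 1.96 × √(0.4125/400) = 6.29, so the crude interval is 5.3% wider.

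**Disagreement between interval and p-value.** Simulation with 4,000 trials per setting compared the adjusted logistic Wald test with whether the crude interval excludes zero. It assumed 5 × 2 strata, region shares 30/40/15/5/10% and 80% seropositive. Stratum effects were none, moderate (MTX stratum rates 41-75%) or strong (24-85%). The strong setting corresponds to s of about 18 points, beyond the table: its width ratio at 62% vs 70% is 1.0825, and √[0.2228 × (1 - 1/1.0825²)] = 0.18.

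| Effect | Sizes | None | Moderate | Strong |
|---|---|---|---|---|
| 62% vs 78% (planned) | 400 vs 400 | 0% | 0% | 0% |
| 62% vs 78% (planned) | 200 vs 400 | 0.2% | 0.1% | 0.3% |
| 62% vs 70% (borderline) | 400 vs 400 | 0.3% | 1.7% | 5.1% |
| 62% vs 70% (borderline) | 200 vs 400 | 1.5% | 1.2% | 4.7% |

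With strong strata every disagreement was p < 0.05 beside an interval containing zero. With non-prognostic strata and 200 vs 400 it ran the other way. That part comes from testing on the log-odds scale and reporting on the risk-difference scale, not from width.

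**Would an adjusted difference help?** A second simulation (2,500 trials per setting, 62% vs 70%, same stratum layout, s = 0 / 6 / 12 points) gave these rates of disagreement with the logistic test:

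| Interval | 400 vs 400 | 200 vs 400 |
|---|---|---|
| Crude | 0.04 / 0.8 / 2.4% | 2.4 / 1.2 / 0.6% |
| Standardised, same model | 0.2 / 0.3 / 0.3% | 2.6 / 2.0 / 2.2% |
| Mantel-Haenszel | 0.7 / 0.9 / 1.1% | 3.6 / 2.9 / 3.5% |

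Monte Carlo error in both simulations is about 0.1 to 0.4 points. A further run with strong strata gave coverage of about 96.3% for the crude interval and about 95% for the standardised one. At 400 vs 400, disagreement fell from 3.2% to 0.3%.

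**The case against.** The strongest reply is that nothing here is wrong. The hypothesis concerns the marginal rates and the crude difference estimates exactly that contrast. Its interval errs, if at all, towards over-coverage. It is a supplementary figure, and the SAP names the logistic p-value as the basis for inference. All of this stands.

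The size can also be challenged, and fairly. The 6% figure needs s = 15 points. If serostatus alone produced it in an 80/20 split, the two serostatus groups would differ in response by 15/√(0.8 × 0.2) = 37.5 points; s = 10 would need 25. Nothing in the documents points to gaps of that size. At s of 3 to 5 points the half-width changes by 0.01 to 0.03 points.

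A reader might infer that the planned intervals are simply too wide. The documents do not support that without a condition, because they give no stratum response rates. A reader might also infer that adjustment makes interval and p-value agree. The simulations show otherwise. The gain is clear at 400 vs 400 with prognostic strata, but at 200 vs 400 the standardised interval disagrees no less often than the crude one.

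What the reply does not answer is why the binary endpoints alone, the primary among them, lack an estimate and interval from the model that tests them. The small cells cited in SAP 6.5 are no obstacle to a standardised difference, since that main-effects model is being fitted anyway.

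**Conclusion.** The mismatch is real for both binary endpoints and its consequences are minor. The crude interval is valid and conservative. Over assumed between-stratum SDs of 0 to 15 points it is about 0 to 6% wider than needed, at most 0.35 points of half-width at 400 vs 400 (6.25 - 5.90). Disagreement with the p-value is confined in practice to borderline comparisons; at the planned 62% vs 78% it is 0% for 400 vs 400 and at most about 0.3% for 200 vs 400.

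It would be a mistake to read this as a threat to the primary conclusion. Type I error and the testing sequence are unaffected, because every decision uses the logistic p-value. All sizes rest on assumed strata, and those for DAS28(CRP) < 2.6 also on assumed response rates.

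**What to change.** In SAP 6.2.3 and 6.3.2, pre-specify as the reported effect estimate the marginal (standardised) risk difference from the logistic model already used for the test, with a delta-method 95% CI, for each filgotinib group against MTX alone. Keep the crude response rates and crude difference as description. Record the change in SAP 6.5.

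Name this one estimator. Mantel-Haenszel weighting should not be offered as an alternative: SAP 6.5 reports small cells in some strata combinations, and in the simulation it disagreed with the test more often than the standardised difference in every setting. Add a sentence that inference rests on the logistic p-value, and that the log-odds test and a risk-difference interval can still differ in borderline cases, especially for the 200-subject arms.

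The cost is SAP wording and standard code, with no new data and no change to sample size or testing order. It should be settled before the Week 24 unblinding, since an adjusted interval chosen afterwards would look selective.

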### **6.2.4. Sensitivity Analysis of the Primary Endpoint**

Sensitivity analyses of the primary efficacy endpoint will be performed.

#### **6.2.4.1. Per-Protocol Analysis**

To evaluate the impact of study conduct on the primary analysis, the proportion of subjects who achieve ACR20 at Week 24 will be analyzed based on the PP Analysis Set as defined in Section 3.1.3 using the logistic regression analysis with NRI for the comparisons of filgotinib dose groups versus MTX alone group. The 2-sided 95% CI of the ACR20 response rate at Week 24 based on normal approximation for each treatment group will be provided.

#### **6.2.4.2. Missing Data Imputation Analyses**

To evaluate the impact of missing data on the ACR20 response rate at Week 24, the following missing value imputation methods will be used:

- The analysis specified in Section 6.2.3 will be performed by using OC and LOCF methods as described in Section 6.1.

- Multiple imputation (MI): The MI procedure replaces each missing binary ACR20 value with a set of plausible values that represent the uncertainty about the right value to impute. Multiple imputed datasets will be generated based on logistic regression models. These multiple imputed data sets are then analyzed by using the method for the primary analysis for complete data as specified in Section 6.2.3. The result of each set of imputed data will be combined using Rubin’s rule {Rubin 1987} and provided. The stratification factors will be included in the imputation model as covariates, and all available data at post-baseline visits up to the time point of interest will be included in the longitudinal model.
- Tipping point analysis: To assess the robustness of analysis results under MNAR (missing not at random) assumption, a delta-adjusting pattern-mixture approach for tipping point analysis {Ratitch 2013} will be conducted for the primary efficacy endpoint. The impact from missing data on the comparisons between filgotinib dose groups versus MTX alone group in ACR20 response rate at Week 24 will be evaluated. Specifically, the proposed method will perform a series of analyses with a range of different values of the shift parameter  $\delta$  applied to the imputed datasets at which the conclusion about the statistical significance of the estimated treatment effect is altered. Each  $\delta$  value is classified as either ‘altering the study’s conclusion’ or tips, ‘keeping the study’s conclusion unchanged’. The tipping points that alter the statistical conclusion will be provided. For each  $\delta$  value, multiple imputed datasets will be generated. The same analysis method for the primary analysis for complete data as specified in Section 6.2.3 will be applied when analyzing adjusted data generated under the different  $\delta$  values.

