#### **6.3.3.2. Missing Data Imputation Analyses**

The following imputation methods will be explored:

- Change from Baseline in the HAQ-DI score at Week 24
  - 1) MI: All subjects with baseline measurement will be included. The MI procedure replaces each missing value with a set of plausible values that represent the uncertainty about the right value to impute. Multiple imputed datasets will be generated based on linear regression models on observed HAQ-DI scores. These multiple imputed data sets are then analyzed by using the analysis method specified in Section 6.3.2 for complete data. The result of each set of imputed data will be combined using Rubin's rule {Rubin 1987} and provided. Stratification factors and baseline values will be included in the imputation model as covariates, and all available data at baseline and postbaseline visits up to the time point of interest will be included in the longitudinal model.
  - 2) Tipping point analysis: All subjects with baseline measurement will be included. To assess the robustness of analysis results for HAQ-DI change from Baseline at Week 24 under MNAR assumption, a set of shift parameter that adjust the imputed values for observation will be examined {Yuan 2014}. The shift parameter that alters the conclusion of the hypothesis testing for HAQ-DI change from Baseline at Week 24 under the MAR assumption will be reported as the tipping point and provided. The tipping point analysis will be conducted by iteratively assigning plausible outcomes to missing values for subjects in different treatment groups independently until the analyses conclusion is reversed. The same analysis method as specified in Section 6.3.2 will be applied when analyzing adjusted data generated under each plausible shift parameter.

- Change from Baseline in mTSS at Week 24
  - 1) MI: Similar MI procedure used for analyzing the change from Baseline in the HAQ-DI score at Week 24 will be performed for change from Baseline in the mTSS at Week 24.
  - 2) Tipping point analysis: Similar tipping point analysis method used for analyzing the change from Baseline in the HAQ-DI score at Week 24 will be performed.
- Proportion of subjects who achieve DAS28(CRP) < 2.6 at Week 24
  - 1) The analysis using the same logistic regression model specified in Section 6.3.2 will be performed by using OC and LOCF methods as described in Section 6.1.

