  - 2) MI: All subjects with baseline measurement will be included. The MI procedure replaces each missing composite DAS28(CRP) value with a set of plausible values that represent the uncertainty about the right value to impute. Baseline value and stratification factors will be included in the imputation model as covariates, and all available data at baseline and all post-baseline visits through the last available visits will be included in the longitudinal model. The multiple imputed datasets will be generated. These multiple imputed data sets are then used to identify subjects with  $\text{DAS28(CRP)} \leq 3.2$  at Week 12, and analyzed by using the analysis method specified in Section 6.3.2 for complete data. The results from each set of imputed data sets will then be combined using Rubin's rule {Rubin 1987}.
  - 3) Tipping point analysis: Similar tipping point method as described in Section 6.2.4.2 will be applied to DAS28(CRP) < 2.6 response rate at Week 24.
- Change from Baseline in SF-36 PCS at Week 24
  - 1) MI: Similar MI procedure used for analyzing the change from Baseline in the HAQ-DI score at Week 24 will be performed.
  - 2) Tipping point analysis: Similar tipping point analysis method used for analyzing the change from Baseline in the HAQ-DI score at Week 24 will be performed.
- Change from Baseline in FACIT-Fatigue at Week 24
  - 1) MI: Similar MI procedure used for analyzing the change from Baseline in the HAQ-DI score at Week 24 will be performed.
  - 2) Tipping point analysis: Similar tipping point analysis method used for analyzing the change from Baseline in the HAQ-DI score at Week 24 will be performed.

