## Appendix 6. SAS Programming for Tipping Point Analysis for Binary Endpoint

The following **%tp\_binary** macro generates multiple imputed data and a set of the shift parameters that adjust the imputed values will be examined.

```

/*-----*/
/*--- Delta-Adjustment Method for Tipping Point Analysis for Binary Endpoint ---*/
/*---
/*--- Generate imputed data set for specified shift parameters ---*/
/*--- data= input data set ---*/
/*--- smin= min shift parameter for active drug ---*/
/*--- smax= max shift parameter for active drug ---*/
/*--- sinc= increment of the shift parameter for active drug ---*/
/*--- pmin= min shift parameter for placebo drug ---*/
/*--- pmax= max shift parameter for placebo drug ---*/
/*--- pinc= increment of the shift parameter for placebo drug ---*/
/*--- trt= treatment group indicator ---*/
/*--- out= output imputed data set ---*/
/*-----*/

%macro tp_binary( data=, smin=, smax=, sinc=, pmin=, pmax=, pinc=, trt=, out=);
  data &out;
  set _null_ ;
  run;

  %let ncase_pbo = %sysevalf( (&pmax-&pmin)/&pinc, ceil );

  %do pc=0 %to &ncase_pbo;

    %let pj= %sysevalf( &pmin + &pc * &pinc);

    /*----- # of shift values -----*/
    %let ncase= %sysevalf( (&smax-&smin)/&sinc, ceil );

    /*----- Imputed data for each shift -----*/
    %do jc=0 %to &ncase;

      %let sj= %sysevalf( &smin + &jc * &sinc);

      proc mi data=&data seed=14823 nimpute=20 out=outmi;
        var trt01pn strat1V strat2V strat3V das28n;
        class trt01pn strat1V strat2V strat3V das28n;
        monotone logistic (das28n / link=glogit);
        mnar adjust( das28n(event='1') / adjustobs=(trt01pn="&trt") shift= &sj)
          adjust( das28n(event='1') / adjustobs=(trt01pn='3') shift= &pj);

      run;

      data outmi;
        set outmi;
        Shift Trt= &sj;
        Shift_Pbo= &pj;

      run;

```

```
data &out;  
    set &out outmi;  
run;  
%end;  
%end;  
%mend tp_binary;
```

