## Appendix 7. SAS Programming for Tipping Point Analysis for Continuous Endpoint

The following %tp\_conti macro generates multiple imputed data sets and a set of the shift parameters that adjust the imputed values will be examined.

```
*****  
/*--- Modified Tipping Point Analysis from Yuan's method ---*/  
/*---  
/*--- Generate imputed data set for specified shift parameters ---*/  
/*--- data= input data set ---*/  
/*--- smin= min shift parameter for active drug ---*/  
/*--- smax= max shift parameter for active drug ---*/  
/*--- sinc= increment of the shift parameter for active drug ---*/  
/*--- pmin= min shift parameter for placebo drug ---*/  
/*--- pmax= max shift parameter for placebo drug ---*/  
/*--- pinc= increment of the shift parameter for placebo drug ---*/  
/*--- trt= treatment group indicator (eg, 1= filgotinib 200 mg) ---*/  
/*--- out= output imputed data set ---*/  
*****
```

```
%macro tp_conti( data=, smin=, smax=, sinc=, pmin=, pmax=, pinc=, trt=, out=);  
  data &out;  
  set _null_ ;  
  run;
```

```
  %let ncase_pbo = %sysevalf( (&pmax-&pmin)/&pinc, ceil );
```

```
  %do pc=0 %to &ncase_pbo;
```

```
    %let pj= %sysevalf( &pmin + &pc * &pinc);
```

```
    /*----- # of shift values -----*/  
    %let ncase= %sysevalf( (&smax-&smin)/&sinc, ceil );
```

```
    /*----- Imputed data for each shift -----*/  
    %do jc=0 %to &ncase;
```

```
      %let sj= %sysevalf( &smin + &jc * &sinc);
```

```
      proc mi data=&data out=all_mono nimpute=15 seed=123;  
        var v_1 v_2 v_3 v_4 v_5 v_6 v_7 v_8 v_9;  
        mcmc chain=multiple impute=monotone;  
      run;
```

```
      proc sort data=all_mono; by _Imputation_ trt01pn; run;
```

```
      proc mi data=all_mono out=outmi seed=465 nimpute=1;  
        by _Imputation_ ;  
        var trt01pn strat1V strat2V strat3V v_1 v_2 v_3 v_4 v_5 v_6 v_7 v_8 v_9;  
        class trt01pn strat1V strat2V strat3V;  
        monotone regression;  
        mnar adjust( v_5 / adjustobs=(trt01pn="&trt") shift=&sj)  
          adjust( v_5 / adjustobs=(trt01pn='3') shift= &pj);
```

```
run;

data outmi;
    set outmi;
    Shift_Trtr= &sj;
    Shift_Pbo= &pj;
run;

data &out;
    set &out outmi;
run;
%end;
%mend tp_conti;
```

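### The multiple imputation models in SAP 6.2.4.2 and 6.3.3.2 do not list randomised treatment, and the first step of the Appendix 7 code omits it; programmed as listed, the MI estimates shrink toward no difference, most of all for mTSS

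*SAP*

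**What the plan says.** SAP 6.2.4.2, MI for ACR20 at Week 24: "The stratification factors will be included in the imputation model as covariates". Post-baseline visit data up to Week 24 also enter the model.

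SAP 6.3.3.2, MI for HAQ-DI: "Stratification factors and baseline values will be included in the imputation model as covariates", again with the visit data. The MI for mTSS, SF-36 PCS and FACIT-Fatigue is defined as similar to this procedure. For DAS28(CRP): "Baseline value and stratification factors will be included in the imputation model as covariates", with visit data.

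No list names treatment, and nothing says that imputation is run separately by arm. The completed data sets are then analysed with the models of 6.2.3 and 6.3.2, which estimate and test the treatment effect.

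The tipping-point code differs from step to step:

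- **Appendix 6 (binary):** "var trt01pn strat1V strat2V strat3V das28n". Treatment (`trt01pn`) is in the model.
- **Appendix 7, first PROC MI:** "var v_1 v_2 v_3 v_4 v_5 v_6 v_7 v_8 v_9" with "mcmc chain=multiple impute=monotone". There is no treatment variable and no BY statement. This step fills only the gaps that stand in the way of a monotone pattern.
- **Appendix 7, second PROC MI:** "var trt01pn strat1V strat2V strat3V v_1 v_2 v_3 v_4 v_5 v_6 v_7 v_8 v_9". Treatment is in the model, and this step imputes values after dropout and applies the shift.

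**The concern.** An imputation model should contain the effect that the completed data will be used to test. If it does not, an imputed value carries the arm difference only so far as the subject's own earlier values carry it. The rest is replaced by an average over all four arms, and the estimated difference shrinks.

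These analyses are there to show whether the conclusions survive missing data. Built-in shrinkage could make a sound result look fragile. It could also set two analyses of one endpoint at odds: the MI result would shrink, while the zero-shift starting point of the tipping-point analysis, whose dropout values condition on arm, would barely do so.

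**Working it through.** **1. The plan's own figure.** SAP 1.3 gives a difference of 0.62 in mTSS change, SD 2.7, 400 per arm and 90% power at two-sided 0.05.

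- n per arm = 2 × (1.960 + 1.282)² × (2.7/0.62)² = 399.
- SE at 400 per arm = 2.7 × √(2/400) = 0.1909.
- Power = Φ(0.62/0.1909 − 1.96) = 90.1%. The plan's figure reproduces.

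**2. mTSS with arm omitted.** Protocol Appendix 2 schedules films at Screening, Week 24 and Week 52/ET. SAP Table 3-4 has no analysis visit between baseline and Week 24; any on-treatment film from Day 15 to Day 267 falls in the Week 24 window. With data up to Week 24 only, no earlier post-baseline value can carry the arm effect. If a share m is missing in each arm, unrelated to outcome, every imputed value is centred on the same pooled mean:

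expected difference = (1 − m) × true difference.

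The documents give no missing-data rate, so m is an assumption.

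| Assumed m | Expected difference | Approximate power |
|---|---|---|
| 0% | 0.620 | 90.1% |
| 5% | 0.589 | 87.0% |
| 10% | 0.558 | 83.2% |
| 15% | 0.527 | 78.8% |
| 20% | 0.496 | 73.8% |

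The power column keeps the complete-data SE, so it isolates the shrinkage. Missing data cost some power even under a correct model. A simulation with Rubin's rule and no informative predictor gave:

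- 10% missing: mean difference 0.557 and power 82% with arm omitted, against 0.622 and 86% with arm included.
- 20% missing: 0.495 and 68%, against 0.619 and 82%.

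**3. ACR20 with arm omitted.** SAP 1.3 assumes 62% against 78%, a difference of 16 points. With no informative predictor, 20% missing would cost 0.20 × 16 = 3.2 points. But the text puts visits in the model, and joint counts are scheduled at six earlier post-baseline visits (Weeks 2, 4, 8, 12, 16 and 20). With all six available and an assumed latent correlation of 0.5 to 0.85, the loss is 0.13–0.40 points at 10% missing and 0.27–0.80 at 20%. So 75–92% of the 3.2 points is recovered (1 − 0.80/3.2 and 1 − 0.27/3.2). Subjects who drop out early have fewer visits. With a single earlier visit, 20% missing gave about 14.2 points (correlation 0.5) or 14.9 (0.8).

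**4. Continuous endpoints with earlier visits.** Suppose k earlier visits carry the same arm difference and share a correlation ρ. The fraction recovered is kρ/(1 + (k−1)ρ) if baseline is uncorrelated with them, and kρ/(1 + kρ) if baseline correlates equally, because baseline carries no arm effect.

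- HAQ-DI (k = 6, ρ from 0.5 to 0.85): lowest 3/4 = 75%, highest 5.1/5.25 = 97%. At 20% missing the loss is 0.6% to 5% of the difference.
- SF-36 PCS and FACIT-Fatigue (Weeks 4 and 12, k = 2): lowest 1/2 = 50%, highest 1.7/1.85 = 92%. The loss at 20% missing is 1.6% to 10%.

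**5. Appendix 7, first step alone.** A simulation of the two-step scheme assumed 2–5% intermittent gaps per visit and 10–20% dropout. The first step filled 1.6–4.5% of the values at the visit of interest, and the overall estimate was 0.98 to 1.01 times the full-data difference. As a rough check, 4.5% of values with a 25% shortfall (the lowest six-visit recovery above) is 0.045 × 0.25 = 1.1%.

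**The case against.** **Silence is not exclusion.** The lists say what will be included and never say that nothing else will be. The code includes treatment in every step that imputes dropout values, so a programmer might well add it to MI. This stands as far as wording goes: treatment is not stated, rather than ruled out. But the lists are specific, no MI code is given beyond the tipping-point macros, and one of those macros leaves treatment out of its first step. A programmer who follows the lists would omit it.

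**The tipping-point analyses.** A reader might infer that these too are pooled across arms and pulled toward no difference. The documents do not support that. Appendix 6 has treatment in both its VAR and CLASS lists, and so does the second step of Appendix 7, where dropout values are drawn and the shift is applied. Only intermittent gaps are filled without arm, and those fills use values on both sides of the gap.

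**Consequence.** These are sensitivity analyses, and for a superiority claim the bias is conservative. Both statements are true. The plan would not overstate robustness on this account; it would understate it. For ACR20 the effect on inference is small even in the worst case of 20% missing with no informative predictor, where power for 400 against 400 stays at 97.8%.

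**Conclusion.** The point holds for the MI analyses as listed, and for the first step of Appendix 7. Its size depends on the endpoint:

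- **mTSS:** the difference shrinks by about the full missing share, to 0.558 at 10% or 0.496 at 20%. This endpoint set the sample size and stands fourth, fifth and eleventh in the testing sequence of SAP 3.5.
- **SF-36 PCS and FACIT-Fatigue:** intermediate, with two scheduled earlier visits.
- **ACR20 and HAQ-DI:** small, because earlier visits recover most of the effect.
- **Appendix 7, first step alone:** about 2% or less.

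The figures rest on assumed missing shares of 5–20%, equal in the arms compared and unrelated to outcome, and on assumed visit correlations. Neither is in the documents. Unequal missingness would change the size of the bias.

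It would be wrong to conclude that the confirmatory results are at risk. The primary test is logistic regression with NRI, the DAS28(CRP) test uses the same method, and the continuous key secondary endpoints are tested by MMRM with treatment in the model. None of these uses the imputation models.

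**What to change.** In SAP 6.2.4.2 and 6.3.3.2, state that randomised treatment is a covariate in every imputation model, or that imputation is done separately by arm. In the first PROC MI of Appendix 7, add treatment indicators to the variable list, or sort the data by treatment and add `BY trt01pn`. The cost is a sentence in each section and a line or two of code. No confirmatory analysis changes.

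One neighbouring mismatch should be handled separately. Appendix 6 has treatment but none of the earlier visits that the MI text of 6.2.4.2 uses. Adding them is not a one-line change: the code uses a MONOTONE statement, so intermittent gaps would first need a step that makes the pattern monotone.
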